- **Denominator:** all in-patients admitted on a ward on the survey day at 8:00 o'clock in the morning. Patients who are admitted on a ward after 8:00 am (8:01 am onward) of the survey day will be excluded from the survey
- **Numerator:** all in-patients admitted on a ward on the survey day at 8:00 o'clock in the morning who are prescribed an antimicrobial agent (s). Patients who are admitted on a ward after 8:00 am (8:01 am onward) of the survey day will be excluded from the survey, even if s/he is on antimicrobial agent (s)
- **On antimicrobial agent (s):**
 - Documented antimicrobial agent (s) on a hospital chart on the survey day. This antimicrobial agent must be prescribed by 8:00am of the survey day
 - No antimicrobial agent is documented on the hospital chart on the survey day but the patient received an antimicrobial agent (s) within the previous 24 hours, or every 48 hours or once a week (any ongoing antimicrobial therapy or prophylaxis)
- **Surgical prophylaxis:** check 24 hours before surgical date to define surgical prophylaxis status as below:
 - Single dose prophylaxis (SP1) – patient received only single dose of antimicrobial agent before surgical procedure
 - One-day prophylaxis (SP2) – patient receives multiple doses of an antimicrobial agent within 24 hours. There are no further doses of prophylaxis after 24 hours
 - > One day prophylaxis (SP3) - patient received an antimicrobial agent as surgical prophylaxis for more than 24 hours (one day), regardless of how many doses a day

- If a patient receives antimicrobial prophylaxis 48 hours before (or earlier) the survey day but no antimicrobial agent in the 24 hours before survey date or on survey day, this patient will be defined as “no antimicrobial agent”
- **Number of beds** = total number of beds in the ward (occupied + empty). Note: number of beds should usually be more than the number of inpatients at 8 o'clock. In case, there is an epidemic of some disease and the number of patients is more than the usual number of beds, count those extra beds (occupied beds + extra beds)
- **Antimicrobial start date:** this should be stated in the patient hospital chart before the survey start. Patients should be prescribed before 8:00am of the survey day. It is required the surveyor to check the previous record in the patient hospital chart

Exclusion criteria

- Patients who are admitted to a ward after 8:00 o'clock (8:01am) in the morning of the survey day

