measured cross-sectionally at month 0, 4, 8, 12 until month 16 after introduction of prescribing guidelines by mobile phone application versus paper-based (30). The model will compare all wedges in the intervention from month 4 to month 16 with all wedges in the reference arm from month 0 to month 12. The duration of exposure of each hospital to the reference or intervention arm will be included in the model as interaction term with the study arm in order to assess whether the duration of exposure is the effect modifier. The model will consider the correlation among the outcome's measurements from the same hospital (cluster) by adjusting for clustering in the model. Odds ratios and the corresponding confidence intervals will be obtained and reported. Tests of significance will be performed at 5% level. Analyses will be done using Stata 15.0 or higher. Likert scale analysis will be used to evaluate prescriber satisfaction with/ acceptability of paper-based compared to mobile phone app delivered antimicrobial prescribing guidelines. The satisfaction/acceptability scale will be assigned in six categories, including strongly agree=5, agree=4, neutral=3, disagree=2 and strongly disagree=1, no opinion/not use=0. Mann-Whitney test will be used to assess the differences between paper-based population and mobile phone app population. AMS knowledge level of prescribers will be assessed using questionnaires based on information in the prescribing guidelines. The overall proportion of correct answers in each time point will be compared (baseline, after paper-based guidelines (before AMS training and introduction of mobile phone app guidelines) and after AMS training and introduction of mobile phone app guidelines). Other factors such as extra AMR training program from hospital/MoH/other organizations, level of education and specialties of prescribers will also be taken into account.

Cost of antibiotic therapy will be calculated from the start date of treatment to the survey day. The unit costs for the antibiotics will be obtained from the [International Medical Product Price Guide](#).

Antibiotic defined daily dose (DDD) will be calculated using data (antibiotic agent, start date, dose and DDD of each antibiotic from www.whooc.no) from PPS in both IPD and OPD. Antimicrobial cost data from participating hospitals will also be collected each hospital pharmacy for comparison with international cost.

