Doses/day						
Route (P, O, R)*						
Diagnosis						
Diagnosis site						
Type of Indication						
Reason in Note (yes/no)						
Is a stop/review date documented? (yes/no)						
Treatment (empiric/targeted)						
The next section is to be filled in only if the treatment choice is based on microbiology data (Treatment=targeted) AND the organism is one of the following						
MRSA (yes/no)						
VRE (yes/no)						
ESBL-producing Enterobacteriaceae (yes/no)						
3rd generation cephalosporin resistant Enterobacteriaceae non-ESBL producing or ESBL status unknown (yes/no)						
Carbapenem-resistant Enterobacteriaceae (yes/no)						
ESBL-producing non-fermenter Gram-negative bacilli (yes/no)						
Carbapenem-resistant non-fermenter Gram-negative bacilli (yes/no)						
Targeted treatment against other MDR organisms (yes/no)						
Targeted treatment against other confirmed laboratory results (yes/no)						
Treatment based on biomarker data (yes/no)						
If yes, which biomarker (CRP, PCT or other)		Value		Unit (in µg/L, mg/L)		

Remark: One In-patient PPS Ward Form is for one ward. One In-patient PPS Patient Form is for one patient who is on antimicrobial agent (s). No In-patient PPS Patient Form will be filled for patients with any antimicrobial agent (s) as defined in this study. * P=Parenteral, O=Oral, R=Rectal.

A3. Outpatient PPS Form

Evaluating the impact of a Lao-language antimicrobial prescribing guidelines on antimicrobial prescribing in Laos

Hospital Antimicrobial Prescribing Survey Form

Outpatient Form

Date of Survey [Add calendar](#) **Surveyor name** [name] [name] _____
 (dd-mmm-yyyy)

Hospital name Mahosot VTP SVK SV XK LNT

OPD/IPD OPD IPD **OPD type** [Drop down list](#)

Total number of consulted patients between 8:00 am and 4:00pm on the day of survey [Numeric](#)

Survey number	Activity	Age (≥2years)	Age (1-23m)	Age (<30days)	Weight (kg)	Gender
	Antimicrobial 1	Antimicrobial 2	Antimicrobial 3	Antimicrobial 4	Antimicrobial 5	
Antimicrobial name						
Single Unit Dose						
Unit (g, mg, IU)						
Doses/day						
Route (P, O, R)						
Diagnosis						
Diagnosis site						
Type of Indication						
Reason in Note (yes/no)						
Is a stop/review date documented? (yes/no)						
Treatment (empiric/targeted)						
If targeted, specify:						
Antimicrobial stop date						

A4. Point Prevalence Survey (PPS) of hospital antimicrobial use Report Format

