Yes No Sometimes

7. How often do you access the provided mobile phone app prescribing guideline?

Daily Nearly every day Weekly Monthly Never

8. How often do you access other prescribing guidelines?

Daily Nearly every day Weekly Monthly Never

9. How would you rate this app overall?

- Very good and I will continue to use it Good but needs a bit more editing and I will continue to use it
 Good but I prefer paper-based version moderate but I prefer paper-based version
 Not good and I prefer paper-based version Others _____

Please give comments to improve this app:

A12. Antimicrobial stewardship (AMS) training

Training objective: to raise awareness of antibiotic good prescribing practices

Trainees: this session will be given to all hospital doctors in all study hospitals at the start of the intervention period of each paired hospital (month 4, month 8 and month 12).

Training date, time and venue: the session will take a maximum of 30 minutes with 10 minutes of discussion/questions. Training date, time and venue will be informed to all doctors one week in advance and again 3 days before starting the session. The session will be run in each hospital separately (2 hospitals on month 4, another 2 on month 8 and the last 2 hospitals on month 12) after conducting point prevalence survey (PPS) of hospital antimicrobial use, completing prescriber feedback survey and after finished introductory session of the prescribing guideline mobile phone App. Verbal consent will be asked from participants to record participant's names, age, sex, working positions, departments, years of work and phone number onto the session registration sheet.

Instructor: the principal investigator of the study will be the training instructor. Training will be given in the format of PowerPoint presentation, followed by question and discussion.

Training material: Handout of the training will be provided to all participants (the same standard session for all hospitals).

Training details: All training details already exist in the prescribing guidelines. The majority of training will be on the section of AMS and some part of the training will be from the therapeutic and prophylaxis sections. This training session will include good practice of antibiotic prescriptions, the idea and benefits of intravenous therapy to oral therapy switch, choice of prescription when patients report penicillin allergy.

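### In-patient cost (and DDDs, if accumulated from the start date) cannot be compared validly between phases, because agents already switched or stopped are not on the survey form; the direction of the bias is not fixed

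*Combined protocol and SAP*

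**What the plan says.** The cost rule in the Statistical analysis section is: "Cost of antibiotic therapy will be calculated from the start date of treatment to the survey day". For DDDs the same section says only that the figure "will be calculated using data (antibiotic agent, start date, dose and DDD of each antibiotic", taken from the surveys in both in- and outpatients. It gives no period over which DDDs are to be added up. Endpoint 5 in section 3.6 is a total cost, app against paper; objective 5 covers both in- and outpatient departments.

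What an in-patient survey captures is set out in section 3.7, Definition for IPD surveys. A patient counts as on treatment if there is a "Documented antimicrobial agent (s) on a hospital chart on the survey day". If nothing is charted that day, there is a fallback: "but the patient received an antimicrobial agent (s) within the previous 24 hours, or every 48 hours or once a week". Prophylaxis that ended earlier is classed as no treatment.

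Form A2 (Appendix A2) has, per agent, a start date, single dose, unit, doses per day and route. It has no stop date and no field for an earlier agent, and it is completed only for patients on an agent. Form A1 holds the ward's total of admitted patients. The outpatient form A3 is the other way round: a stop date and no start date, although section 3.7 lists a start date among the items collected in both settings.

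Appendix A12 says that the training given on entry to the intervention phase covers "the idea and benefits of intravenous therapy to oral therapy switch".

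**The concern.** The cost rule looks back over a treatment history, but the form holds only its current end. If a patient has moved from an intravenous to a different oral agent, only the oral agent is listed, counted from its own start. The 24-hour look-back does not rescue the intravenous agent, because it applies only when nothing is charted on the survey day. If a patient has stopped treatment, there is no form and the recorded cost is zero. The hospital pharmacy cost data do not fill the gap: the plan collects them for comparison with international prices.

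The lost cost would matter less if it were the same in both phases. It is unlikely to be, since switching is one of the behaviours taught with the app. The trial intends to report antibiotic cost under app and paper guidelines, and a comparison that depends on how much history each phase has lost does not answer that question.

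**Working it through.** The plan states no cost or DDD figure, so there is none to reproduce. Course length, switch day, price ratio and switching rates are not in the documents; all values below are assumptions.

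**One patient.** Intravenous cost 1 unit/day, oral cost b = 0.1 to 0.5, survey on day 6.
- Paper patient never switches: recorded 6, true 6. App patient switches after day 3: recorded 3b, true 3 + 3b. Recorded saving 6 − 3b = 4.5 to 5.7; true saving 3 − 3b = 1.5 to 2.7. Ratio 2.1 (b = 0.1) to 3.0 (b = 0.5).
- Same pair surveyed on day 4: recorded 4 − b = 3.5 to 3.9; true 1 − b = 0.5 to 0.9. Ratio 4.3 to 7.0.
- Paper patient switches after day 3, app patient after day 1, survey on day 6: recorded 3b against 5b, so the app looks dearer by 2b = 0.2 to 1.0. True cost is 3 + 3b against 1 + 5b, a saving of 2 − 2b = 1.0 to 1.8. The sign is reversed over the whole price range.

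**Phase level.** Let the survey fall uniformly within a course of T = 7 days, intravenous until day S at price 1, then oral at price r. Setting r = 1 represents DDDs with equal daily DDD.
- True course cost: S + r(T − S).
- Recorded total under the plan, for the current agent from its own start: S²/2 + r(T − S)²/2. Without a switch: T²/2 = 24.5.

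Example with S = 3, r = 0.1, against no switching: true 1 − 3.4/7 = 51.4%; recorded 1 − (4.5 + 0.8)/24.5 = 78.4%. In general, against a phase with no switching, recorded minus true saving is s(1 − s)(1 + r) with s = S/T, which is always positive. Against a phase that already switches, it is not.

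| Assumed change, reference to intervention | r | True saving | Recorded saving |
|---|---|---|---|
| Share switching on day 3: 10% to 30% | 0.1 | 10.8% | 17.0% |
| Same, DDDs | 1 | 0% | 10.3% |
| All switch: day 5 to day 3 | 0.1 | 34.6% | 58.3% |
| All switch: day 3 to day 1 | 0.3 | 33.3% | 14.5% |
| All switch: day 3 to day 1 | 0.5 | 20.0% | −11.8% |
| All switch: day 4 to day 2, DDDs | 1 | 0% | −16.0% |

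First row: true 1 − (0.7 × 7 + 0.3 × 3.4)/(0.9 × 7 + 0.1 × 3.4) = 1 − 5.92/6.64; recorded 1 − (0.7 × 24.5 + 0.3 × 5.3)/(0.9 × 24.5 + 0.1 × 5.3) = 1 − 18.74/22.58. Fifth row: true 1 − 4/5; recorded 1 − 9.5/8.5.

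**Stopping rather than switching.** Shortening one agent from 7 to 5 days truly saves 2/7 = 28.6%. The survey total shows 1 − 25/49 = 49.0%; the mean per treated patient shows 28.6%. If half the courses last 2 days and half 8 days, and the short ones are avoided, the true saving is 20.0%. The survey total shows 1 − 16/17 = 5.9%, and the mean per treated patient rises from 3.4 to 4.0, or −17.6%.

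**Survey-day quantity.** In the same model the numbers found on intravenous and oral treatment are proportional to S and T − S. Expected survey-day cost is therefore proportional to S + r(T − S), the true course cost. It returns the true saving in every row of the table and in both stopping examples.

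**The case against.** The strongest objection concerns direction. A reader might infer that the missing cost always favours the app. The documents do not support that. It requires reference patients who rarely switch, and Appendix A12 says that the training content is already in the guidelines, which reference-phase prescribers hold on paper. If they already switch and training only brings the switch forward, the saving can be understated or reversed. This objection stands.

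A reader might also take the 2- to 7-fold figures as the size of the bias. They compare one patient who switches with one who never does. The assumed rise from 10% to 30% gives about 1.6-fold (17.0/10.8).

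A third inference would be that DDDs are definitely summed from start date to survey day. Start date is a listed input, but no window is given, so the DDD part is conditional.

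The cost rule could also be read as counting the current agent from the start of treatment as a whole. The earlier intravenous days would then be charged at the oral price: in the example with S = 3 and r = 0.1 the recorded saving is 1 − 6.5/24.5 = 73.5% against 51.4%. Cost is still wrong, although DDDs at equal daily DDD would not be.

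Finally, the lost-agent mechanism is confined to in-patients, and a survey-day figure would miss the duration of an outpatient prescription. Both points stand and limit the fix. None of this restores the missing in-patient history.

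**Conclusion.** The concern holds for in-patients. The start-to-survey-day sum cannot be formed correctly from form A2, and the error is likely to differ between phases because switch training comes with the intervention. Endpoint 5 is affected; endpoint 1 is affected if DDDs are accumulated from the start date. Savings are overstated if training makes more patients switch, and may be understated or reversed if it mainly makes existing switches earlier or avoids short courses. Without switching rates or a stated summary measure, neither size nor sign can be fixed from the documents. The figures rest on an assumed 7-day course, assumed switch days and price ratios, and a steady state.

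For outpatients the fault is different: the start-date rule cannot be applied to form A3 at all.

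**What to change.** **In-patients.** Replace the start-to-survey-day sum with the survey-day quantity. For each agent in use under the survey definition, take single dose × doses/day × unit cost (or divide by the DDD instead of multiplying by unit cost). Add over agents, count untreated patients as zero, and divide by all in-patients on form A1. State how agents given every 48 hours or weekly convert to a daily amount. Drop start date as an input to cost and DDDs. Reword endpoints 1 and 5, in the synopsis and section 3.6, as DDDs and cost per in-patient-day.

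**Outpatients.** Compute the prescribed quantity from survey date to stop date on form A3 and report it separately. Say what is done when no stop date is documented, which the form itself allows for.

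**Cost.** Text changes only; the fields needed are already on A1, A2 and A3. The in-patient result is per patient-day, not per course. It does not capture changes in length of stay or treatment after discharge, so cost per course should not be reported from the in-patient surveys. Adding earlier agents to A2 would not be enough by itself: with full history still cut at the survey day, the 51.4% example would read 1 − 17.3/24.5 = 29.4%.

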Although the severity of the AMR situation in Laos remains lower than elsewhere in Asia, misuse of antimicrobials is a major driver of resistance. This is a therefore an important opportunity for implementation of a simple technology, which may help reduce further worsening of the AMR situation. Antimicrobial prescribing apps are a promising tool to improve prescribing. However, there has been no evidence from trials to support whether the antimicrobial prescribing guidelines in the format of a mobile phone application are superior to conventional means (i.e. paper-based) in low- and middle-income countries (LMIC). This trial could have a significant impact in Laos and in other LMICs, and inform policy globally, by improving prescribing and hence reducing AMR.

II. Study objectives and hypothesis

Study objectives

Primary objective

To compare the proportion of antimicrobial prescriptions adherent with prescribing guidelines delivered by mobile phone application (app) versus paper-based prescribing guidelines in both in- and outpatients in six general hospitals in Laos

Secondary objectives

1. To compare the change in antimicrobial defined daily doses (DDDs) after introduction of paper-based versus mobile phone app prescribing guidelines plus antimicrobial stewardship (AMS) training in both in- and out patients

2. To compare the change in proportion of patients receiving intravenous antimicrobials route between paper-based and mobile phone app prescribing guidelines + AMS training in both in- and out patients
3. To compare the AMS knowledge level of the prescribers before and after prescribing guidelines delivered by mobile phone app and AMS training
4. To compare the prescriber satisfaction with/acceptability of paper-based prescribing guidelines versus mobile phone app prescribing guidelines
5. To compare antimicrobial costs before and after prescribing guidelines delivered by mobile phone app and AMS training in both in- and outpatient departments
6. To compare the proportion of patients admitted to hospital receiving an antimicrobial prescription before and after introduction of the paper-based prescribing guidelines; and the mobile phone app prescribing guidelines + AMS training

III. Methods

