3.5 Study intervention and reference

Before starting the project, PI, co-investigators and research team will visit each participating hospital to discuss about the project's objectives and how we would like to conduct this project during 16 months to the directors of the hospitals. These six hospitals have already participated in Global PPS, led by the PI and research team of this project. Hospital staff will be informed about the study by the PI and a director of hospital (also co-investigator) before starting the project and all prescribers in participating hospitals will be encouraged to participate in the training and surveys.

a. Pre-study phase

Four participating hospitals (MS, XK, LNT and SV) in this study have already participated in Global-PPS since 2017, whilst VTP participated in 2018 and SVK in 2019. Antimicrobial prescription data of all six hospitals are available for the whole of 2019. This is the period when there were no available Lao therapeutic and prophylactic antimicrobial prescribing guidelines. These data will be used in this project to compare the change in proportion of antimicrobial prescriptions and the change in administration route before and after the introduction of the prescribing guidelines (both paper-based and mobile phone app versions). To be able to answer our study question, Lao therapeutic and prophylactic antimicrobial prescribing guidelines were developed to be introduced at month 0 of the project. Details of Lao therapeutic and prophylactic antimicrobial prescribing guidelines are described below.

Lao antimicrobial prescribing guidelines

Lao National antimicrobial prescribing guidelines are based on existing Lao treatment guidelines, current data on infectious disease pathogens and antimicrobial susceptibility patterns in Laos and international antimicrobial prescribing/treatment guidelines (e.g. WHO, CDC, NICE, ISID, Sanford). The guidelines are separated into paediatric and adult guidelines for ease of use. These guidelines include recommendation for therapy, prevention and antibiotic stewardship.

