3.6 Endpoints

Primary endpoint

The proportion of antimicrobial prescriptions adherent with prescribing guidelines delivered by mobile phone app versus paper-based prescribing guidelines at month 16 (12 months' exposure in each group)

Secondary endpoints

1. Total antimicrobial defined daily doses (DDDs) prescribed in mobile phone app versus paper-based groups of 12 months' exposure in each group

2. Proportion of patients prescribed antimicrobials by the intravenous route in mobile phone app versus paper-based groups of 12 months' exposure in each group
3. AMS knowledge level of prescribers prescribed in mobile phone app versus paper-based groups of 12 months' exposure in each group
4. Prescriber satisfaction/acceptability of the prescribing guidelines in mobile phone app versus paper-based groups of 4 months' exposure in each group
5. Total costs of antimicrobial prescribed in mobile phone app versus paper-based groups of 12 months' exposure in each group
6. Proportion of patients admitted to hospital receiving an antimicrobial prescription before and after introduction of the paper-based prescribing guidelines; and the mobile phone app prescribing guidelines + AMS training of 12 months' exposure in each group

Definitions of adherence to the guidelines

1. Full adherence with the guidelines = using correct antimicrobial agent (s) and correct dose based on the provided antimicrobial prescribing guidelines
2. Partial adherence with the guidelines = using correct antimicrobial agent (s) with incorrect dose based on provided antimicrobial prescribing guidelines
3. Non-adherence with the guidelines = using a different antimicrobial agent (s) compared to that suggested in provided antimicrobial prescribing guidelines

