1. Mahosot Hospital - 16 wards, including infectious disease paediatrics, general paediatrics, neonatal-paediatric intensive care unit (ICU), ICU adult, general medicine, gastro-intestinal, cardiovascular, infectious disease adult, lung, psychology, ear-nose-throat (ENT), abdominal surgery, uro-surgery, plastic surgery, general surgery, post operation room, obstetrics and gynaecology (OBGY)
2. LNT provincial hospital - 7 wards, including medicine, surgery, paediatrics, OBGY, intensive care unit, ENT
3. XK provincial hospital - 11 wards, including cardiology, infectious disease, OBGY, ICU adult, ICU paediatrics, surgery, post operation, medicine, eyes, and specialty ward (mixture of medicine, surgery, OBGY or paediatric patients – this ward is for patients who need private and more comfortable room)
4. VTP provincial hospital - 5 wards, including paediatrics, OBGY, medicine, surgery and ICU
5. SVK provincial hospital - 9 wards, including medicine 1, medicine 2, lung, infectious diseases (HIV/AIDs ward), surgery, OBGY, ICU and specialty ward
6. SV provincial hospital - 7 wards, including medicine 1 (general medicine), medicine 2 (mostly infectious disease patients), lung, paediatrics, surgery, OBGY and ICU

Survey dates and times – PPS will be conducted every four months throughout the year. There will be 5 PPS in total from the start of the project (month 0) until the finish date of the project (month 16) (Figure 2).

PPS must be completed within a maximum of 5 consecutive working days from the start date of collecting data in hospital of that PPS round. All hospital charts of all admitted patients on a ward must be screened at 8 o'clock in the morning on the day of the survey. Survey days will be from Monday to Friday, excluding public holidays.

Survey staff

- Research staff, *OR*

- Local doctor who is familiar with their own local hospital charts and has been trained on data collection for this project

Inclusion and exclusion criteria

Inclusion criteria

1. All patient hospital charts from all in-patient wards at 8:00 o'clock in the morning of a survey day will be counted as the denominator
2. All patient hospital charts from all in-patient wards with any kind of antimicrobial agent (s) prescribed at 8 o'clock in the morning of a survey day will be counted as numerator.

Definition for IPD surveys

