
Surveyor qualification

- Research staff, *OR*
- Local doctor who received training for data collection for this project

Inclusion and exclusion criteria

Inclusion criteria

1. All patients consulting at OPD of paediatrics, medicine and surgical wards of all participating hospitals during 8:00am and 4:00pm of a survey day will be counted as the denominator

2. All patients consult at OPD of these three wards of all participating hospitals who are prescribed antimicrobial (s) between 8:00am and 4:00pm on a survey day will be counted as the numerator
3. If the same outpatient comes back for consultation during the same survey period (same round, any day during these five days) this patient will also be included in the survey and be defined as a new consultation.

Definitions for OPD surveys

- **Denominator:** all outpatients who consult at paediatrics, medicine and surgical OPDs on the survey day between 8:00am and 4:00pm for 5 consecutive working days. Patients who come outside this period of time will be excluded from the survey
- **Numerator:** all outpatients who consult at paediatrics, medicine and surgical OPDs and are prescribed antimicrobial (s) on the survey day between 8:00am and 4:00pm for 5 consecutive working days. Patients who come outside this period of time will be excluded from the survey, even if they are prescribed any antimicrobial (s).

Exclusion criteria

- Patients who come for consultation outside the survey time (before 8:00am or after 4:00pm) of the survey day
- Patient who are prescribed topical antimicrobial (s) only will be excluded from numerator but they will still be in the denominator

Study setting

OPD PPS will be conducted for 5 consecutive working days. Hospital directors of each hospital will be informed three days before the survey. Head of OPD will be informed about the survey on the same day as they survey day. Data will be collected from an OPD prescription sheet at the OPD pharmacy. There will not be any private discussion or interview of patients or doctors.

The OPD prescription sheet from patients will be scanned and saved as an electronic file for data entry by research staff on the same day. The reason for scanning OPD prescription sheets is to avoid disrupting the OPD workflow of the rush hours of each participating hospital. The total number of OPD patients (denominator) will be collected from the OPD logbook at the end of each survey day.

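### Secondary endpoint 1 applies one fixed DDD per drug to children and adults alike with no age split, so a difference in paediatric share between app and paper surveys shows up as a difference in consumption

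*Combined protocol and SAP*

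**What the plan says.** The first secondary objective is "To compare the change in antimicrobial defined daily doses (DDDs) after introduction of paper-based versus mobile phone app" guidelines with stewardship training, in inpatients and outpatients. Section 3.6 turns this into "Total antimicrobial defined daily doses (DDDs) prescribed in mobile phone app versus paper-based groups", without an age restriction and without a denominator. The Statistical analysis text in section 3.7 gives the method: "Antibiotic defined daily dose (DDD) will be calculated using data (antibiotic agent, start date, dose and DDD of each antibiotic from www.whooc.no"). The same sentence takes the data from both settings: "DDD of each antibiotic from www.whooc.no) from PPS in both IPD and OPD".

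Children are in those data. In the inpatient survey, Mahosot lists two paediatric wards and a neonatal-paediatric intensive care unit; Luang Namtha, Vientiane Provincial and Salavan list paediatric wards, and Xiengkhuang a paediatric intensive care unit. The outpatient denominator is "all outpatients who consult at paediatrics, medicine and surgical OPDs on the survey day between 8:00am and 4:00pm". Section 3.5 says of the prescribing guidance that "The guidelines are separated into paediatric and adult guidelines for ease of use".

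Age and body weight are recorded for each patient (section 3.7). The only age breakdown planned is descriptive: the hospital report in Appendix A4 tabulates patients by age band and shows prescriptions by class for those aged 15 or under and those over 15. The logistic mixed model is for adherence. No model is given for DDDs.

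**The concern.** Dividing by one DDD per drug puts all patients on one scale, whatever dose their age calls for. If a treated child receives on average fewer DDDs than a treated adult, a survey with more children gives a lower figure per patient even when every prescription is unchanged.

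The two conditions are not balanced in calendar time. Paper surveys come earlier and app surveys later, each round is a fresh cross-section, and rounds are four months apart. A difference in age mix between the two sets of surveys would therefore pass into the comparison of consumption, which is the first secondary objective. No period or hospital terms are specified for DDDs that might absorb part of it.

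**Working it through.** The plan states no expected DDDs, variance or power for this endpoint, so there is no figure to reproduce. The check is of the mechanism and its possible size.

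**Inputs.** From the documents: surveys at months 0, 4, 8, 12 and 16; the allocation in Figure 2; and the bed numbers in the hospital descriptions of section 3.2 (50, 150, 450, 100, 200 and 70; total 1,020). Assumed, because the documents give neither: *s*, the paediatric share of treated patients, and *r*, mean DDDs per treated child divided by mean DDDs per treated adult.

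**Step 1: one survey against another.** DDDs per treated patient, relative to an adult, are 1 − s(1 − r). With prescribing unchanged within each age group,

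apparent change = [1 − s₁(1 − r)] / [1 − s₀(1 − r)] − 1.

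| r | s 20% → 30% | s 20% → 40% |
|---|---|---|
| 0.20 | 0.76/0.84: −9.5% | 0.68/0.84: −19.0% |
| 0.33 | −7.7% | −15.5% |
| 0.50 | −5.6% | −11.1% |
| 0.70 | −3.2% | −6.4% |

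The change is zero only if r = 1 or s is constant. These are shifts between two surveys, not app against paper.

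**Step 2: app against paper under a seasonal pattern.** Months 0 and 12 fall in the same season, as do months 4 and 16; month 8 stands alone. In Figure 2, leaving out month 0, the hospital-surveys are:

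| | Month 4 | Month 8 | Month 12 | Month 16 | Total |
|---|---|---|---|---|---|
| Paper | 6 | 4 | 2 | 0 | 12 |
| App | 0 | 2 | 4 | 6 | 12 |

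The month 4/16 season supplies 6 of 12 in each condition. The conditions differ only in that two of twelve hospital-surveys lie in a different season.

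The largest fall with equal hospital weights has a share of 20% at month 8 and 30% otherwise:

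- paper share = (8 × 30% + 4 × 20%)/12 = 26.7%
- app share = (10 × 30% + 2 × 20%)/12 = 28.3%
- at r = 0.20: (1 − 0.283 × 0.8)/(1 − 0.267 × 0.8) − 1 = −1.7%; at r = 0.33: −1.4%

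The largest rise (20% at month 12, 30% otherwise) is +1.7%. Counting month 0 as paper does not raise the maximum. With 20% versus 40% the extremes are −3.6% and +3.8%.

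With bed weights, over all six orders of the three pairs and with or without month 0, the maxima are 3.1% and 6.7%. The 3.1% arises with the order north, south, centre, month 0 counted as paper, and a share of 20% at months 4/16 and 30% otherwise:

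- paper bed-surveys = 1,020 + 1,020 + 820 + 550 = 3,410, of which 1,020 (month 4) are at 20%: share 27.0%
- app bed-surveys = 200 + 470 + 1,020 = 1,690, of which 1,020 (month 16) are at 20%: share 24.0%
- at r = 0.20: (1 − 0.240 × 0.8)/(1 − 0.270 × 0.8) − 1 = +3.1%

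**Step 3: what this bound leaves out.** It assumes the same seasonal share at every hospital. A sustained trend would not cancel in this way. Nor would a lasting difference between hospitals: over months 4 to 16 the first pair contributes one paper and three app rounds, the last pair three and one. If the pairs had shares of 40%, 30% and 20% in order of crossover (assumed), equal numbers and r = 0.25, the paper share would be (40 + 2 × 30 + 3 × 20)/6 = 26.7% and the app share (3 × 40 + 2 × 30 + 20)/6 = 33.3%. The artefact would be 0.75/0.80 − 1 = −6.3%.

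**Step 4: a raw total.** Take 80 adults and 20 children, r = 0.25: 80 + 5 = 85 adult-equivalents. If children replace adults until the share is 30%, the total is 70 + 7.5 = 77.5 (−8.8%). If the 80 adults stay and children are added to reach 30% (34.3 children), the total is 80 + 8.6 = 88.6 (+4.2%), although the figure per treated patient again falls by 8.8%. For an undivided total the sign is not fixed.

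**The case against.** The strongest reply is about size. A reader might infer from step 1 that the app/paper comparison could be off by 8% to 19%. The documents do not support that: it would need every paper survey at the lower share and every app survey at the higher one, and the schedule balances the month 4/16 season exactly between the conditions. This stands, and it is why the seasonal figures here are the smaller ones.

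A second reply is that several premises are inferred. The plan never says that adult and child DDDs are added together; that follows from the word total, the inclusion of paediatric units and the absence of any split. Nor does it say that children are dosed by weight or that a DDD is an adult-dose unit. This also stands, but the mechanism needs only one divisor per drug and a mean dose that differs by age.

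Third, Appendix A4 would show a shift in age mix at each survey. It would, but seeing the shift does not remove it from the endpoint. Fourth, restricting the endpoint to adults would drop children from the first secondary objective, although the paediatric guideline is part of what is tested. That is a fair point against an adults-only endpoint, but not against stratified reporting.

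**Conclusion.** The concern holds as a minor flaw in the stated method for one of six secondary endpoints. Followed as written, the plan makes the DDD comparison depend on the age mix of the surveys. For a purely seasonal change in share between 20% and 30%, common to all hospitals, with r between 0.20 and 0.33, the crude artefact in DDDs per treated patient is at most about 2% (equal weights) or 3% (bed weights). For 20% versus 40% it is about 4% or 7%. All values of s and r are assumptions, and a milder r gives less. A sustained trend, or differences in share between hospitals, could give more; the documents neither show nor exclude these. For a raw total, even the direction depends on whether children replace adults or are added to them.

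It should not be read as a criticism of the primary endpoint or of the sample size, neither of which uses DDDs. Nor does it show that consumption in children should go unreported.

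**What to change.** State in the Statistical analysis section that DDDs will be computed and compared separately for patients over 15 years and for those aged 15 or under (the cut already used in Appendix A4), each per 100 patients surveyed in that age group. Interpret the older stratum as DDD consumption. For children, also report the proportion treated and the number of agents per 100 patients surveyed. A change in paediatric share alone then produces no change within either stratum; a shift in age within the younger group can still move its DDDs, which is why the two further measures are needed there.

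Age is already collected, so this is a change of wording with no new data, visits or power calculation. The cost is that there is no single overall DDD figure and that each stratum is estimated less precisely. The split should be fixed before analysis, so that it is not chosen after seeing the results.
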